# 6 STATISTICAL CONSIDERATIONS

## 6.1 General Considerations

Data summaries are tabulated by appropriate grouping for each analysis population as specified in Section [5.3](#).

Continuous endpoints are summarized by descriptive statistics including number of non-missing observations (n), mean, standard deviation (SD), median, minimum, and maximum. Categorical variables are summarized by frequency counts (n) and percentages of subjects (%) in each category, including missing or unknown when appropriate. Unless otherwise specified, confidence intervals (CIs) are two-sided with 95% confidence.

All derivations, statistical analyses, summaries, and listings are generated using SAS Version 9.4 or higher (SAS Institute, Inc., Cary, North Carolina, United States).

Anti-SARS-CoV-2 Immunoglobulin Intravenous (Human) (NP-028), abbreviated as COVID-HIG  
EBS-CVH-006 Statistical Analysis Plan

## 6.2 Units and Precision

All clinical laboratory data and vital sign data are reported using standard international units. Measures with non-standard units include:

- Anti-SARS-CoV-2 immunobinding IgG assay titer: AU, binding antibody titer normalized to reference standard.

Safety variables (i.e., clinical laboratory values, vital signs) including derivations thereof are reported to the same precision as the source data. Anti-SARS-CoV-2 immunobinding IgG assay titers are reported with one decimal place or two significant digits (e.g., 0.032, 18.0).

All PK concentrations are reported in listings and analyzed with the same precision as the source data provided by the bioanalytical laboratory. For derived PK parameters, the following conventions are used:

- Elapsed time from dosing is expressed as hours in the calculations and rounded to two decimal places.
- Parameters derived directly from source data (e.g.,  $C_{max}$ ,  $t_{max}$ , minimum, maximum) or first-order statistics (e.g., mean) are reported and analyzed with the same precision as the source data.
- Second-order statistics (e.g., SD) are reported with one more significant digit than the source data.
- Percentages are reported to one decimal place.
- Ratios of means for PK parameters are presented with two decimal places.

## 6.3 Derived Variables

This section provides definitions of derived variables. In some cases, the definitions are provided in the relevant sections.

**AE, causing discontinuation of study treatment**, is defined as one with action taken of “Drug Withdrawn” on the AE eCRF.

**AE, causing study discontinuation**, is defined as a Yes response to the corresponding question on the AE eCRF.

**AE, medically attended (MAAE)**, is defined as a Yes response to the corresponding question on the AE eCRF.

**AE, related**, is defined as one that is “possibly,” “probably,” or “definitely” related to IP per Investigator assessment on the eCRF. If the relationship is missing for one or more occurrences of an AE for a given subject, the closest relationship of the remaining occurrences of the AE for that subject is used; if the relationship is missing for the only occurrence of an AE for a given subject, then that event is excluded from summaries by relationship.

**AE, resulting in death**, is defined as a Fatal outcome response on the AE eCRF.

Anti-SARS-CoV-2 Immunoglobulin Intravenous (Human) (NP-028), abbreviated as COVID-HIG  
EBS-CVH-006 Statistical Analysis Plan

**AE, serious**, is defined as a Yes response to the corresponding question on the AE eCRF, based on the individual criteria that make an AE qualify as serious (results in death, is life-threatening, requires inpatient hospitalization or prolongation of existing hospitalization, results in persistent or significant disability/incapacity or is a congenital anomaly or birth defect, or any event that may require medical or surgical intervention to prevent one of these outcomes).

**AE, severity**, was graded Grade 1 (mild) to Grade 5 (death) as described in Section 5.8. If the severity is missing for one or more occurrences of an AE for a given subject, the maximum severity of the remaining occurrences of the AE for that subject is used; if the severity is missing for the only occurrence of an AE for a given subject, then that event is excluded from summaries by severity.

**AE, special interest**. There were no AEs of special interest in this study.

**AE, treatment emergent**. AE collection began after screening. AEs occurring after a subject has given informed consent, but before dosing, are excluded from summaries unless the condition worsened during or after dosing. Only treatment-emergent AEs are summarized.

**Age** at screening visit is automatically calculated by EDC based on date of birth versus date of informed consent.

**Age group** is defined in this study as ages 18 to 35 and 36 to 59 years.

**Analysis visits** are defined in Section 5.4.

**Analysis populations** are defined in Section 5.2.

**Baseline** is defined in Section 5.5. Change from baseline is defined as (value at post-baseline assessment – value at baseline).

**Baseline seronegative stratum** is defined as subjects with undetectable SARS-CoV-2 antibody (<LLOQ) at screening on the Diasorin LIAISON SARS-CoV-2 S1/S2 IgG antibody assay.

**Baseline seropositive stratum** is defined as subjects with detectable SARS-CoV-2 antibody ( $\geq$ LLOQ, but  $\leq$ 80 AU/mL) on the Diasorin LIAISON SARS-CoV-2 S1/S2 IgG antibody assay.

Note that, if a subject is randomized into a stratum and their antibody status is later corrected such that s/he should have been placed into the other stratum, the subject is analyzed according to the corrected stratum for PK analyses but as randomized for baseline and efficacy analyses.

**Body mass index** at screening visit is automatically calculated by EDC as a subject's weight in kg divided by height in  $m^2$ .

**Cohort** is defined as the cohort specified for the subject on the corresponding eCRF.

**Completion of study** for an individual subject is defined as completion of the Day 57 visit and any required safety follow-up (i.e., a disposition status of completed).

**Completion of study medication treatment** is defined by the answer to the eCRF question, "Did the infusion/injection progress as planned?"

**Early withdrawal** for an individual subject is defined as completion of the Withdrawal Visit (i.e., a disposition status other than completed).

Anti-SARS-CoV-2 Immunoglobulin Intravenous (Human) (NP-028), abbreviated as COVID-HIG  
EBS-CVH-006 Statistical Analysis Plan

**Enrolled/randomized** is defined as receipt of a randomization number assignment within the EDC system.

**Medical history** items entered on the medical history eCRF will be considered to predate the study regardless of onset date.

**Medication, concomitant**, is defined as one taken after start of IP administration on Day 1 (baseline) through the end of study. For analysis purposes, any medication which is ongoing or with a stop date that is on or after the start date of the dosing is categorized as a concomitant medication. Partial or missing concomitant medication start and/or end date are imputed according to Section [6.5.1](#).

**Medication, prior**, is defined as one with a stop date within 30 days prior to the screening visit (60 days for COVID-19 vaccination) through the start of IP administration on Day 1 (baseline).

**Protocol deviations** are defined by inclusion in the EDC protocol deviation module (subject-level only, not site-level), including monitor-identified deviations as well as EDC system-identified programmatic deviations. Protocol deviations are classified by category and type (important/not important).

**Rounding of values** is described in Section [6.2](#).

**Study Day 1** is defined as the day of IP administration on Day 1 (baseline). The day prior to Day 1 is Day -1. There is no Day 0. If the subject was not treated, then the Day 1 (baseline) is defined as the day of randomization.

Study day relative to Day 1 is calculated as:

- **Study Day** = (assessment date – date of Day 1 + 1) if the assessment is on or after Day 1.
- **Study Day** = (assessment date – date of Day 1) if the assessment is before Day 1.

For conversion of durations, 1 year = 365.25 days and 1 month = 365.25/12 = 30.4375 days.

**Summary statistics** are described in Section [6.1](#).

**Time duration (in days) between event A and event B** is (date of event B – date of event A + 1). For conversion of durations, 1 year = 365.25 days and 1 month = 365.25/12 = 30.4375 days.

**Treatment, actual**, is defined as the treatment administered to the subject by the site (i.e., corresponding to the kit number used).

**Treatment arm or group** is defined as IM, SC, or IV administration route.

**Treatment, randomized**, is defined as the treatment assigned to the subject by the EDC (i.e., corresponding to the kit number assigned).

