### **3.3 Safety Endpoints**

The following safety endpoints were evaluated:

- AEs within 72 hours post-dosing
- AEs and SAEs in healthy adults up to 56 days post-administration of a single COVID-HIG dose (changed from to 84 days post-administration in Protocol Amendment 3.0)

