### 6.5.2 Missing Outcome and Covariates

Subjects are included in the analyses to the extent of their available data; missing PK and efficacy data are not imputed. See Section 5.4.

Subjects with missing categorical data are counted in missing or unknown categories when appropriate. Subjects with missing numeric data are treated as missing completely at random when calculating summary statistics. For likelihood-based analyses (e.g., regression), missing at random is assumed.

Anti-SARS-CoV-2 Immunoglobulin Intravenous (Human) (NP-028), abbreviated as COVID-HIG  
EBS-CVH-006 Statistical Analysis Plan

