### 9.2.1 Overall Summary of Adverse Events

An overall summary of AEs is provided by SOC, PT, and treatment arm for the Safety population. The events are sorted in descending frequency of subjects in the ‘Total’ column for SOC, then PT, unless otherwise specified. Each of the line items below on the AE summary is a separate tabulation as well.

- Any AE
- Related AEs
- AEs occurring within 72 hours post-dosing
- Related AEs occurring within 72 hours post-dosing
- Grade 3 or higher AEs
- Grade 3 or higher related AEs
- MAAEs
- Related MAAEs
- SAEs
- Related SAEs
- COVID-19 AE and COVID-19 SAE
- AEs leading to death
- AEs leading to discontinuation of study treatment
- AEs leading to study withdrawal

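### SAP 6.3 drops a sole-occurrence AE with missing relationship or severity from the related-AE and severity summaries, so those counts can be understated with nothing in the table to show it

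*SAP*

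**What the plan says.** SAP 6.3 gives two parallel rules. If relationship is missing for the only occurrence of an AE in a subject, "then that event is excluded from summaries by relationship". If the grade is missing for the only occurrence, "then that event is excluded from summaries by severity". If the subject has other occurrences of the same AE, the event stays in. For relationship, "the closest relationship of the remaining occurrences of the AE for that subject is used"; for grade, "the maximum severity of the remaining occurrences of the AE for that subject is used".

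SAP 9.2.1 has 14 line items, each also a separate table. Six are defined by relationship, grade or both: related AEs, related AEs within 72 hours, Grade 3 or higher AEs, "Grade 3 or higher related AEs", related medically attended AEs and related SAEs. Protocol 9.4.3.2 also plans a summary of treatment-emergent AEs and SAEs by severity.

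The safety endpoints in SAP 3.3, which protocol 3.2.3.1 calls primary, are "AEs within 72 hours post-dosing" and "AEs and SAEs in healthy adults up to 56 days post-administration of a single COVID-HIG dose". The protocol synopsis adds AEs that lead to stopping or suspending administration. None of these depends on relationship or grade. SAP 9.2 also provides a listing of every AE by subject.

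**The concern.** Safety is a primary objective, and protocol 1.6 hypothesises that all three routes are well tolerated. The related-AE and Grade 3 or higher rows will inform that judgement. Leaving an unassessed event out of the numerator while the subject stays in the denominator treats the event, in effect, as unrelated or as below Grade 3. For an absolute incidence that is the less cautious choice. A reader of the table could not tell that it had been made without reconciling the table against the listing.

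The SAP is more cautious about timing. Under 6.5.1, an AE with a wholly missing start date is dated to first dosing, so it counts as treatment-emergent. No reason is given for handling relationship and severity differently.

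**Working it through.** The plan states no AE rate, no missing-data rate and no sample size calculation, so there is no figure of its own to reproduce.

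**Step 1. Direction of the exclusion.** Take one AE that is the subject's only occurrence of that term, with one field missing. The table gives the count under SAP 6.3 minus the true count.

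| Missing field | Truth | Affected row | Any AE, 72 h and SAE rows |
|---|---|---|---|
| Relationship | Related | Related: 0 − 1 = −1 | 0 |
| Relationship | Unrelated | Related: 0 − 0 = 0 | 0 |
| Severity | Grade 3 or 4 | Grade 3 or higher: 0 − 1 = −1 | 0 |
| Severity | Grade 1 or 2 | Grade 3 or higher: 0 − 0 = 0 | 0 |

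The error in an affected row is −1 or 0. In a by-severity table the preferred-term cells can likewise only lose. At system organ class level, a subject with another, lower-graded AE moves to that lower grade.

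**Step 2. Size.** SAP section 4 gives 7 to 8 subjects per arm and 23 in all; I assume that all were dosed. One subject contributes 100/n percentage points:

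- n = 8: 100/8 = 12.5
- n = 7: 100/7 = 14.3
- n = 23: 100/23 = 4.3

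For illustration, suppose that one subject's only related (or only Grade 3 or higher) AE has the field missing. The documents do not say how often this would happen. Exact (Clopper-Pearson) 95% intervals are:

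| n | SAP rule | Event counted |
|---|---|---|
| 8 | 0/8 = 0% (0 to 36.9) | 1/8 = 12.5% (0.3 to 52.7) |
| 7 | 0/7 = 0% (0 to 41.0) | 1/7 = 14.3% (0.4 to 57.9) |
| 23 | 0/23 = 0% (0 to 14.8) | 1/23 = 4.3% (0.1 to 21.9) |

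The fall occurs only if two conditions hold: the event was truly related (or Grade 3 or higher), and the subject has no other qualifying event in that row. Otherwise the arm-level row is unchanged.

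**Step 3. Comparison of routes.** Suppose that 2 of 8 subjects truly have a related AE in both the IM and IV arms, and one of the IV events has no relationship recorded. The true difference is 2/8 − 2/8 = 0. Under the SAP rule it is 2/8 − 1/8 = +12.5 points, so IM looks worse. The direction of a between-route error depends on which arm has the missing value.

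**Step 4. Start-date rule, for contrast.** An AE with no start date is dated to dosing. If its true onset was before dosing, the treatment-emergent and 72-hour rows each gain 1. If it was after 72 hours, the 72-hour row gains 1. The primary-endpoint rows can therefore err upward.

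**The case against.** The strongest reply is that the rule leaves the endpoints alone and will hardly ever operate. Protocol 8.1.8 requires the investigator to grade all AEs. Protocol 8.1.9 requires a causality assessment, with a second, independent one by the medical monitor for SAEs. The investigator signs the eCRFs (10.3), monitors check them against source (11.1), and every AE is listed. All of this stands, and it makes the expected effect small. It does not make the affected tables transparent when a field is missing.

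A reader might also infer a contradiction with SAP 6.5.2, which states: "Subjects with missing categorical data are counted in missing or unknown categories when appropriate". The documents do not support that. SAP 6.5 expressly sends AEs with missing relatedness or severity to 6.3, so 6.3 is the specific rule, and 6.5.2 is general and qualified. What remains is an unexplained departure from the general approach.

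The rule for repeated occurrences is a weaker target. It takes the closest relationship or highest grade on record, so a subject's overall maximum is wrong only if the missing occurrence was worse than every recorded one. The borrowed value can also exceed the truth for that occurrence. In a row with a second condition, such as onset within 72 hours, this could even raise a count. The one-way statement is therefore confined to the two exclusion clauses.

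Finally, counting missing relationship as related replaces a possible undercount with a possible overcount. That is true, but the overcount would be disclosed and is the cautious direction for a safety table.

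**Conclusion.** The point holds for the six relationship- or grade-dependent rows of SAP 9.2.1 and for the by-severity summary. The exclusion clauses can understate absolute counts in the related and Grade 3 or higher rows, cannot overstate them, and leave no trace in the table. The fall is 12.5 points (n = 8) or 14.3 points (n = 7) for one affected subject, under the two conditions in the working. It should be rare, so this is a low-cost correction of modest priority.

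Two stronger readings are tempting. A reader might infer that the primary safety tables are affected. They are not, because those endpoints are all AEs and SAEs regardless of relationship or grade, and their rows keep the event. A reader might also infer that error in the safety analysis always favours the product. That fails as well: the start-date rule can push primary-endpoint rows upward, and the direction of a route comparison depends on where the missing value falls.

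**What to change.** In SAP 6.3:

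- Delete the two exclusion clauses.
- For missing relationship, state that an AE with no relationship recorded for its only occurrence is counted as related, with a footnote giving the number so imputed in each arm. Say that this is for tabulation only, because protocol 8.1.9 puts any event not rated possible or probable on the unrelated side for reporting.
- For missing severity, show such events in a 'Missing/Unknown' row, and give a sensitivity count for the Grade 3 or higher rows that treats them as Grade 3.

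The cost is two sentences in the SAP, plus a row and a footnote in the table shells. If no field is missing, no result changes. The downside is that related-AE counts may be slightly overstated: an imputed event that was truly unrelated adds one subject to a row unless that subject already counts there.

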## 6.4 Statistical Hypotheses

No formal statistical hypotheses are tested in this Phase 1 study; all analyses are descriptive.

Anti-SARS-CoV-2 Immunoglobulin Intravenous (Human) (NP-028), abbreviated as COVID-HIG  
EBS-CVH-006 Statistical Analysis Plan

## 6.5 Handling of Missing Data and Other Data Issues

This section describes the handling of missing data, and other data issues. Please see Section 6.3 for assumptions for AEs with missing relatedness and/or severity. Note that the handling of data issues for PK data is described in Section 8.4.4.

Unless otherwise specified, no imputation is performed for missing data and complete data analyses are used whenever possible.

### 6.5.1 Missing or Partial Dates

For missing or partial dates for AEs, medical history (or prior diagnosis), and prior and concomitant medications, the following conventions are used for the purpose of determining whether the AE is treatment-emergent, duration since prior diagnosis of the disease, and whether the medication/therapy is concomitant or not. Original values are provided in the listings as is, without imputation.

- For start date missing completely or missing the year, impute the date to the date of first exposure to any study treatment.
- For start date missing both the month and the day, if the year is the same as the date of first exposure to any study treatment, impute the date to the date of first exposure to any study treatment, otherwise, impute the date to January 1st.
- For start date missing the day only, if the year and the month are the same as the date of first exposure to any study treatment, impute the date to the date of first exposure to any study treatment, otherwise, impute the date to the first of the month.
- For end date missing completely or missing the year, impute the date to the date of last contact.
- For end date missing both the month and the day, if the year is the same as the date of last contact, impute the date to the date of last contact, otherwise, impute the date to December 31st.
- For end date missing the day only, if the year and the month are the same as the date of last contact, impute the date to the date of last contact, otherwise, impute the date to the last day of the month.

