6 STUDY PROCEDURES AND ASSESSMENTS PER VISIT

6.1 Screening

Screening period is within 14 days prior to Day 1.

Eligible participants will first undergo informed consent counseling. Once informed consent has been obtained, participants will undergo a screening visit to ascertain their eligibility in this study. The Screening visit assessments will include:

- Written informed consent.
- Collection of demography information (date of birth, sex, race/ethnicity, height, body weight, BMI).
- Review of inclusion/exclusion criteria.
- Medical history and ongoing medications.

Anti-SARS-CoV-2 Immunoglobulin Intravenous (Human) (NP-028), abbreviated as COVID-HIG
EBS-CVH-006, Version 3.0, 18 Feb 2022

- Perform rapid SARS-CoV-2 IgM/IgG antibody test and SARS-CoV-2 antigen test prior to collecting other samples. Only proceed further with screening assessments if negative for SARS-CoV-2 IgM and antigen.
- Complete physical examination: to include assessment of general appearance, and the following body systems: head-neck, respiratory, cardiovascular, gastrointestinal, dermatological, lymphatic/hematological, musculoskeletal, neurological, metabolic/endocrine.
- For WOCBP: assess contraception use (>30 days prior to dosing) and instruct on use of contraception from the time of Screening through end of study (up to Day 57).
- Serum pregnancy test for WOCBP and FSH testing for post-menopausal women.
- Vital signs (resting ≥ 10 minutes) include body temperature, pulse, respiratory rate, sitting blood pressure, and SpO₂ (pulse oximetry).
- Local safety laboratory assessments:
 - Chem 7 panel [Na⁺, K⁺, Cl⁻, HCO₃⁻, BUN, creatinine, glucose], total and direct bilirubin, ALT, AST, LDH.
 - CBC (red blood cells, white blood cells, hemoglobin, hematocrit) with differential (neutrophils, eosinophils, basophils, monocytes, lymphocytes).
 - Urinalysis.
- Viral marker testing [Human immunodeficiency virus 1/2 (HIV 1/2) antibody, HBV surface antigen, HCV antibody].
- Urine drug screening (e.g., amphetamines, barbiturates, benzodiazepines, cannabinoids, cocaine opioids).
- Nasopharyngeal swab sample for SARS-CoV-2 RT-PCR test.
- Serum sample for the Diasorin LIAISON SARS-CoV-2 S1/S2 IgG antibody test.
- Provide counselling to participants on precautions/measures to prevent contracting SARS-CoV-2 infection.
- Assess for any COVID-19 symptoms or SARS-CoV-2 exposure.
- Monitor/assess AEs related to study procedures.

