8 SAFETY ASSESSMENTS AND REPORTING

The safety of COVID-HIG will be assessed by collection of AEs, laboratory test results (blood chemistry and hematology, urinalysis), concomitant medications, vital signs, and physical exam results.

The occurrence of AEs will be monitored throughout all phases of the study and will cover all participating subjects. Any medical history changes that occur after screening but before dosing will be captured as an AE. Any AE that occurs after screening but before dosing will be documented in the source documents and captured in EDC if subject is randomized. Capture of treatment emergent adverse events (TEAEs) starts from the time of COVID-HIG administration and until the end of study period (up to Day 57 visit). Unanticipated problems related to study procedures may be collected following enrollment.

Adverse events are to be elicited by the investigator (or designate) by asking the participant non-leading questions. The association of the AE to COVID-HIG is to be judged by the investigator as related or unrelated (see Section 8.1.9 below).

Anti-SARS-CoV-2 Immunoglobulin Intravenous (Human) (NP-028), abbreviated as COVID-HIG
EBS-CVH-006, Version 3.0, 18 Feb 2022

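### SAP 6.5.1 imputes incomplete AE start dates without checking the end date, so an AE that ended before dosing can be counted as treatment-emergent

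*SAP*

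**What the plan says.** SAP 6.5.1 states what its date conventions are for: "the following conventions are used for the purpose of determining whether the AE is treatment-emergent", along with time since prior diagnosis and whether a medication is concomitant. Three rules cover incomplete start dates:

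- Date or year missing: "For start date missing completely or missing the year, impute the date to the date of first exposure to any study treatment".
- Month and day missing: "For start date missing both the month and the day, if the year is the same as the date of first exposure", the start becomes the dosing date; otherwise it becomes 1 January of the recorded year.
- Day missing: "start date missing the day only, if the year and the month are the same as the date of first exposure", the start becomes the dosing date; otherwise it becomes the first of the recorded month.

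The end-date rules are separate bullets, and nothing links the two sets.

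SAP 6.3 defines treatment emergence: "AEs occurring after a subject has given informed consent, but before dosing, are excluded from summaries unless the condition worsened during or after dosing". SAP 9.2 puts only treatment-emergent AEs in the summary tables.

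Pre-dose AEs do reach the database. Protocol section 8 says: "Any AE that occurs after screening but before dosing will be documented in the source documents and captured in EDC if subject is randomized". On the length of that period, Protocol 6.1 says: "Screening period is within 14 days prior to Day 1".

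**The concern.** Setting an uncertain start to the dosing date is a sound default when the event could have begun after dosing. It is not sound when the record shows that the event was already over. In that case the rule overrides recorded data, and SAP 6.5.1 and SAP 6.3 give opposite answers for the same event with no stated precedence.

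Treatment-emergent status decides which AEs enter the summaries behind the primary safety endpoints (Protocol 3.2.3.1; SAP 3.3). Arms of 7-8 participants (SAP 4) leave little room to absorb a wrongly counted participant.

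**Working it through.** The plan gives no figure on this point and has no sample-size calculation, so there is nothing to reproduce. The check applies the three start-date rules as written.

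**1. One record.** Inputs (illustrative): dosed 20 January 2022; AE start recorded only as January 2022; AE end 14 January 2022.

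- The year and month match dosing, so the imputed start is 20 January 2022.
- SAP 6.3 defines duration as end date minus start date plus 1. Here that is 14 − 20 + 1 = −5 days.
- The imputed start is on the dosing date, so the AE is called treatment-emergent, although it ended six days before dosing. SAP 6.3 would exclude it.

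**2. How often the rule misfires, given such a record.** Assumptions: every dosing date in a window is equally likely, and so is every onset from 14 days before to 56 days after dosing. The documents give a December 2021 start, a 1.5-month enrolment period and a protocol version dated 18 February 2022, but no dosing dates, so two windows were tried:

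- 1 December 2021 to 31 January 2022: 62 dosing dates × 14 pre-dose days = 868 pre-dose combinations.
- 1 December 2021 to 18 February 2022: 80 × 14 = 1,120 pre-dose combinations.

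| Missing part of start date | Pre-dose AEs called treatment-emergent, first window | Second window |
|---|---|---|
| Day | 658/868 = 75.8% | 805/1,120 = 71.9% |
| Month and day | 763/868 = 87.9% | 1,015/1,120 = 90.6% |
| Whole date | 868/868 = 100% | 1,120/1,120 = 100% |

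These shares apply only to pre-dose AEs whose start date is incomplete. They are not error rates for the trial.

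**3. Direction.** Post-dose onsets called not treatment-emergent: 0 of 62 × 57 = 3,534 and 0 of 80 × 57 = 4,560, for every missing-date pattern. The rule can add events but cannot lose them.

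**4. Effect of an end-date condition.** If each pre-dose AE has a known end date before dosing and that date is checked, false treatment-emergent calls fall to 0/868 and 0/1,120 in all three patterns. No post-dose AE changes class, because none can end before dosing.

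**5. Size in a table.** One participant is 1/8 = 12.5 or 1/7 = 14.3 percentage points of an arm. SAP 9.2 counts a participant once per preferred term and once per system organ class, so the shift appears only where that participant has no other event in the row.

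**The case against.** The strongest reply is that this is a conservative rule in a descriptive Phase 1 study. It never loses a post-dose event. The pre-dose period is at most 14 days and ends with an overnight clinic stay at which AEs are assessed, so a pre-dose AE with a known end but an incomplete start should be unusual. SAP 6.3 already points to the right classification. Listings show the original dates, and the AE listing flags events that are not treatment-emergent (SAP 9.2). SAP 1 says that programmer's notes in the table shells hold further derivation details. Those notes are not available here and may contain a check.

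Most of this stands, and it limits the point to a small correction. It does not remove it. Conservatism justifies resolving doubt toward counting, but an AE with a recorded end before dosing leaves no doubt. Listings let a reader find the error but do not correct the table. SAP 1 also calls the shells working documents that can be updated, so the rule belongs in the SAP.

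Two stronger readings are tempting, and neither is supported:

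- **Medical history.** SAP 6.3 says "items entered on the medical history eCRF will be considered to predate the study regardless of onset date", from which a reader might infer that post-dose events can be hidden as history. But history is taken at Screening and updated on Day -1 (Protocol Table 2, footnote 1), both before dosing. New observations and deteriorations after dosing must be reported as AEs (Protocol 8.1.1 and 8.2). Only a post-dose event filed on the wrong form would be lost, which is a data-entry error. The clause also keeps undated history items from being treated as starting at dosing.
- **The 72-hour endpoint.** A reader might infer that a misdated AE also counts as occurring within 72 hours of dosing. SAP 6.5.1 lists the uses of its conventions, and this is not one of them. Nothing in the documents says that imputed dates set that window.

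**Conclusion.** The concern holds in a narrow form. As written, SAP 6.5.1 can give an AE a start date after its own recorded end and call it treatment-emergent, which contradicts SAP 6.3. The error is one-directional, toward over-counting. It requires three things together: a pre-dose AE, an incomplete start date, and an end date that places the event before dosing. The documents do not say how many such records exist; few should be expected.

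Given a pre-dose AE with an incomplete start, the rule misfires in roughly 72-76% of cases when only the day is missing, 88-91% when month and day are missing, and always when the whole date is missing. The first two ranges depend on the assumed dosing windows and uniform timing; the last does not. One affected participant with no other event in the row shifts that arm's incidence by 12.5 to 14.3 points. The documents do not support saying that AEs are being misclassified in this trial, or that the date rule drops any.

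**What to change.** Keep every existing start-date rule in SAP 6.5.1 and add:

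*If the AE end date (complete, or partial but with known parts that place it before first dosing) is before first dosing, the AE is not treatment-emergent, and an imputed start date may not be later than the end date.*

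The partial-end wording matters when the start is wholly missing: an AE with an end recorded only as December 2021 and dosing on 20 January 2022 would otherwise still be given a start of 20 January.

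The addition should not be paired with a catch-all that sends all remaining incomplete starts to the dosing date, because that would override the first-of-month and 1 January branches. With dosing on 15 January 2022, an ongoing AE whose start is known only as December 2021 is correctly placed before dosing now, and a catch-all would make it treatment-emergent. The medical-history clause needs no change on this account.

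The cost is one sentence and one programming check. The default toward counting remains wherever onset after dosing is possible. An AE whose end date is also missing, or too incomplete to place it before dosing, is handled as now.
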